#### 1.3 Subgroup definitions

The primary endpoint, selected secondary endpoints and selected safety endpoints will be evaluated using the subgroups defined in

Table 1-1. Subgroup analyses for the study endpoints are represented in Table 1-2.

Table 1-1 Subgroup definitions

Subgroup variables	Categories	Description	Label for outputs	Suffix for outputs
Country	Participating countries 		Region	а
Randomization weight stratum	Body weight strata: <90 kg, ≥90 kg) and < Tertile 1, ≥ Tertile 1 and < Tertile 2, ≥ Tertile 2		Weight strata	b
Gender	Male, female		Gender	С
Age	< 65 years, ≥ 65 years and < 75 years, ≥ 75 years		Age	d
Smoking status	Current smoker, Current Non- smoker (i.e. never smoked or former smoked) at screening		Smoking status	е
PASI at baseline	PASI ≤ 20,PASI > 20		PASI category	f
BSA and PASI at baseline	Moderate psoriasis ((BSA ≥ 10% or PASI ≥ 10) and BSA ≤ 20% and PASI ≤ 20), severe psoriasis (BSA > 20% or PASI > 20)		Severity of psoriasis	g
Psoriatic Arthritis at Baseline	Yes, No		Psoriatic Arthritis	h
Previous psoriasis therapy	Yes, No Failure * (Yes, No) e number of patients per country, some of	Any previous psoriasis therapy discontinued within 5 years prior to Screening * at least one therapy with lack of efficacy or lack of tolerability	Previous psoriasis therapy	i

## Table 1-2 Subgroup analyses

Endpoint/ analysis	Region	Weight strata	Gender	Age	Smoking status	category	Severity of psoriasis	arthritis	Previous psoriasis therapy
Subject disposition	X								
Demography & baseline characteristics	Х								
Study medication: duration of exposure	Х								
Maintaining of PASI 90	Х	Х	Х	Х	Х	Х	Х	Х	Х

22-May-2017 (12:05)

Endpoint/ analysis	Region	Weight strata	Gender	Age	Smoking status	PASI category	Severity of psoriasis	arthritis	Previous psoriasis therapy
response									
PASI 50, 75, 90, 100 response at Week 52	X	×	X	X	X	Х	X	Х	X
AEs by SOC- PT	Х	Х							
SAEs by SOC- PT	Х								
AEs study- drug related (investigators assessment)	Х								

#### 1.4 Assessment windows, baseline and post baseline definitions, missing data handling

#### 1.4.1 Assessment windows

At each visit, all study assessments should be completed prior to any potential application of the study treatment. Visit windows are described below.

#### 1.4.2 Study Day 1 and other study days

The first day of administration of study treatment (first dose) is defined as Study Day 1 or *Dav 1*.

All other study days will be labeled relative to Day 1. For event dates on or after Day 1, study day for a particular event date is calculated as [Date of event] - [Date of first dose]+1, i.e., Day 2, Day 3, etc., will be one day, two days, etc., after Day 1, respectively.

For the dates before Day 1, study day for an event date is calculated as [Date of event] – [Date of first dose], i.e., Day -1, Day -2, etc., will be one day, two days, etc., before Day 1, respectively. Duration of an event will be calculated as (Event end date – Event start date + 1).

The term "Day 0" will not be used.

#### 1.4.3 Screening, baseline and post-baseline definitions

Screening refers to any procedures (e.g., checking inclusion and exclusion criteria) performed prior to the date of visit 2. Per protocol, subject informed consent must be obtained prior to performing any study related activity. The date of signing informed consent is the start date of screening period. Any assessment obtained during the screening period will be labeled screening assessment.

Visit 2 is defined as *Baseline* visit. All consecutive visits are labeled according to the preplanned study week where they occur, i.e. Week 1, Week 2, and so on.

Week 24 is defined as the end of Treatment Period 1 (visit 11) for patients without premature discontinuation during Treatment Period 1. For patients with premature termination within Treatment Period 1 the last visit is defined as end of Treatment Period 1.

Week 52 is defined as the end of Treatment Period 2 (visit 18) for patients without premature discontinuation during Treatment Period 2. For patients with premature termination in Treatment Period 2 the last visit is defined as end of Treatment Period 2.

Any visits and assessments occurring after the end of Treatment Period 2 visit (Week 52 in the eCRF) will be aligned to the Week 60 Follow-Up visit.

#### 1.4.4 Analysis Visits windows

*Visit-windows* will be used for the data that is summarized by visit; they are based on the study evaluation schedule and comprise a set of days around the nominal visit day. The visit windows for Treatment Period 1 and Treatment Period 2 are shown in Table 1-3. In this table, the days are counted since the first dose of study treatment (study days).

When visit windows are used, all visits will be re-aligned, i.e., they will be mapped into one of the visit windows. E.g., if the *Week 4* visit of a subject is delayed and occurs on Day 46 instead of on Day 29, say, it will be re-aligned to visit window *Week 8*. In the case of major deviations from the visit schedule, or due to unscheduled visits, several assessments of a subject may fall in a particular visit window (either scheduled or unscheduled). Statistical approaches to handle multiple assessments in a given visit window are specified in Section 1.4.5.

Table 1-3 Analysis windows for scheduled visits

Analysis Visit	Week	Scheduled Day	Analysis Window
Screening	-4 to BSL		-28 days to Day 1
Baseline*	BSL	1	
Week 1	1	8	Day 2-11
Week 2	2	15	Day 12-18
Week 3	3	22	Day 19-25
Week 4	4	29	Day 26-43
Week 8	8	57	Day 44-71
Week 12	12	85	Day 72-99
Week 16	16	113	Day 100-127
Week 20	20	141	Day 128-155
Week 24	24	169	Day 156-183**
Week 28	28	197	Day 184-211
Week 32	32	225	Day 212-239
Week 36	36	253	Day 240-267
Week 40	40	281	Day 268-295
Week 44	44	309	Day 296-323
Week 48	48	337	Day 324-351
Week 52	52	365	Day 352-379

\* Baseline measurement before the first drug administration. The days are counted since the first dose of study treatment.

For parameters which are not collected at every visit (e.g. DLQI, WPAI-PSO), visit windows defined in Table 1-3 will be combined. For example, if a parameter is measured at Week 24, Week 36 and Week 48, but not in between (i.e. Week 28, Week 32, Week 40 and Week 44), the Week 36 visit window will extend from Day 212 to Day 295 (combining Week 32 to Week 40 visit windows). If more than one assessment falls into the interval, the rules defined in Section 1.4.5 below are applied.

Assessments from Treatment Period 2 will not be considered for Treatment Period 1 and Treatment Period 1 visits will not be mapped into Treatment Period 2. For example, if a Week 28 (scheduled visit) measurement falls into the Week 20 visit window, this measurement would not be analyzed as Treatment Period 1 value.

#### 1.4.5 Multiple assessments within visit windows

When there are *multiple assessments* in a particular visit window, the following rules are applied to select one value "representing" the subject in summary statistics in a visit window.

For baseline assessment definition see Section 1.4.3. For post-baseline visit windows the following applies (unless otherwise specified):

• for *quantitative variables*, the *closest* to the actual visit is chosen. If two assessments have the same distance, then the earlier one will be chosen.

\*\* Data assessed after the date of the Week 24 dose will not be considered as "Week 24 data"

- for *qualitative variables*, the *worst* record is selected. It is noted that in the analyses performed, *worst* case is always well defined (e.g., for urine protein values "+" and "++", the worst case is defined as "++")
- in case qualitative variables are based on quantitative variables, e.g. PASI 75 response, the
  visit will be assigned to the quantitative variable, and this visit will be used for the derived
  qualitative variable

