with the protocol, except for the chest X-ray or TB work-up, if applicable, if performed not more than 12 weeks prior to Day 1 (Baseline). If patients do not have a chest X-ray available within 12 weeks of the projected Day 1 date, the X-ray should be performed after it is certain the patient meets inclusion/exclusion criteria in order to minimize unnecessary exposure to radiation.

If the date of the TB work-up is less than 12 weeks from Baseline then the TB work-up does not have to be repeated; however, the patient must repeat the QFT performed by the central laboratory.

During the Treatment Periods 1 and 2, patients may be seen at an unscheduled visit, eg, if they experience deterioration of psoriasis or suspected AEs. During these unscheduled visits, study drug will NOT be administered.

Recommended visit windows

Treatment periods:

- ± 2 days for Baseline, Week 1, Week 2, Week 3 and Week 4 and for Week 24.
- ± 2 days for all study drug home administrations.
- \pm 5 days for all other study visits.
- Visit 1 and Visit 2 must not be conducted at the same day and all relevant information for Visit 2 must be available before treating the patient. The screening period might not be longer than 4 weeks.

For patients who discontinue study drug prematurely before the end of the Treatment Period 1 for any reason other than withdrawal of informed consent, the Week 24 (planned EOT1) visit must be performed at least 28 days (4 weeks) after the last drug administration and the patient should then enter the treatment free follow-up period, if applicable.

For patients who discontinue study drug prematurely before the end of the Treatment Period 2 for any reason other than withdrawal of informed consent, the Week 52 (planned EOT2) visit must be performed at least 28 days (4 weeks) after the last drug administration and the patient should then enter the treatment free follow-up period, if applicable.

If a patient refuses to return for these assessments or is unable to do so, every effort should be made to contact them, or a knowledgeable informant, by telephone or by sending appropriate correspondence (ie, certified letter) immediately. At this contact, the safety (eg, potential occurrence of AEs or SAEs) and the primary reason for the patient's premature withdrawal should be determined. Documentation of attempts to contact the patient should be recorded in the patient source documents.

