#### 1.5.2 Background and demographic characteristics

The following common background and demographic variables will be analyzed:

- Age (which is derived from date of birth and the date of screening visit)
- Age categories (<65 years,  $\ge 65$  years and <75 years,  $\ge 75$  years)
- Gender
- Race

- Height
- Weight at Baseline
- Weight categories at Baseline (< 90kg, ≥ 90kg)

- Body mass index at Baseline (BMI)
- Smoking status at screening visit (never, current, former)
- Smoking amount: estimated amount consumed (in pack years) for current smokers
- Time since stop of smoking until screening visit (years)
- Tuberculosis (TB) status at Baseline (no TB present, active TB diagnosed, latent TB diagnosed)
- Initiation of TB therapy according to local guidelines (yes, no) for patients with latent TB

The Body Mass Index (BMI) at Baseline will be calculated using the following formula:

BMI 
$$(kg/m^2) = (body weight in kilograms at V2) / (height in meters)^2$$

For BMI, the body weight used is the last value prior to treatment start. If there is no weight recorded prior to taking of study treatment, BMI will be missing.

Psoriasis specific baseline characteristics and history of disease will be summarized as well:

- Baseline PASI
- Baseline PASI categories ( $\leq 20, \geq 20$ )
- Baseline IGA mod 2011 score (almost clear, mild disease, moderate disease, severe disease)
- Body Surface Area (BSA) affected by plaque-type psoriasis at baseline
- Time since occurrence of plaque psoriasis (years between start date and date of screening visit)
- Presence of psoriatic arthritis
  - time since occurrence of psoriatic arthritis (years between start date and date of screening visit)

Unless otherwise specified, summary statistics will be presented for continuous variables for all subjects in the SAF-TP1 and for each treatment group and for all subjects (total) in the FAS-P90R and the FAS-P75R.

The number and percentage of subjects in each category will be presented for categorical variables for all subjects in the SAF-TP1 and for each treatment group and for all subjects (total) in the FAS-P90R and the FAS-P75R.

Smoking history will be analyzed separately for former and current smokers. No statistical tests for comparability of baseline characteristics will be performed.

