#### Overview of analysis methods for efficacy variables Table 1-7

Variable(s)	Summary statistics for binary/ categorical data	Risk Difference	Logistic regression	Summary statistics for continuous data	Analysis of Co- variance	Time to event data analysis
PASI 90 response at Week 52 for patients with PASI 90 response at Week 24	Х	Х	Х			
PASI 90 response at Week 52 for patients with PASI 75 response but without PASI 90 response at Week 24	X	Х	Х			
PASI 50/75/90/100 response from Week 28 to Week 52 (or Week 60)	X	X				
IGA mod 2011 0 or 1 response from Week 28 to Week 52 (or Week 60)	Х	Х				
Time course of PASI from Week 24 to Week 52 and change of PASI compared to baseline				X	Х	
Time course of DLQI from Week 24 to Week 52 and change of DLQI compared to baseline				Х	Х	
Time course of DLQI 0 or 1 from Week 24 to Week 52	Х	Х				
Time course of EQ-5D-5L from Week 24 to Week 52 and change of EQ-5D-5L compared to baseline	Х			X	Х	
Time course of WPAI-PSO from Week 24 to Week 52 and change of WPAI-PSO compared to baseline				X	Х	
Time course of assessment of pain itching and scaling from Week 24 to Week 52 and change of this assessment compared to baseline				X	X	
PASI 50, 75, 90 and 100 response at Week 24	Х					
IGA mod 2011 0 or 1 response at Week 24	Х					
Time to PASI 90 response from Week 24 on for patients with PASI 75 response but without PASI 90 response at Week 24						X
Time to loss of PASI 75 response from Week 24 on for patients with PASI 75 response but without PASI 90 response at Week 24						Х
PK data and PASI response during course of the study						
Time to loss of PASI 90						Х

Variable(s)	Summary statistics for binary/ categorical	Risk Difference	Logistic regression	Summary statistics for continuous	Analysis of Co- variance	Time to event data analysis
	data			data		
response after Week 24 for patients with PASI 90 response at Week 24						
Time to loss of IGA mod 2011 0/1 response after Week 24						Х
Body Surface Area affected by plaque-type psoriasis at Week 52 and change from baseline				Х		
Time course of PASI from Baseline to Week 24 and change of PASI compared to baseline				Х		
PASI 50/75/90/100 response from Week 1 to Week 20	X					
IGA mod 2011 0 or 1 response from Week 1 to Week 20	X					
Time course of DLQI from Baseline to Week 24 and change of DLQI compared to baseline				Х		
Time course of EQ-5D-5L Baseline to Week 24 and change of EQ-5D-5L compared to baseline				X		

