#### 1.8.1.2 Definition of IGA mod 2011 score and IGA mod 2011 0 or 1 response

The IGA mod 2011 rating scale for overall psoriatic disease (shown in Table 1-9) has been developed based on a previous version of the scale used in AIN457 phase II studies, and has been updated in collaboration with health authorities. The explanations/descriptions of the points on the scale have been improved to ensure appropriate differentiation between the points.

The IGA mod 2011 used in this study is static, i.e., it refers exclusively to the subject's disease state at the time of the assessments, and does not attempt a comparison with any of the subject's previous disease states, whether at baseline or at a previous visit.

Table 1-9 The IGA mod 2011 rating scale

Score	Short Description	Detailed Description
0	Clear	No signs of psoriasis. Post-inflammatory hyperpigmentation may be present.
1	Almost clear	Normal to pink coloration of lesions; no thickening; no to minimal focal scaling.
2	Mild	Pink to light red coloration; just detectable to mild thickening; predominantly fine scaling.
3	Moderate	Dull bright red, clearly distinguishable erythema; clearly distinguishable to moderate thickening; moderate scaling.
4	Severe	Bright to deep dark red coloration; severe thickening with hard edges; severe / coarse scaling covering almost all or all lesions.

Note: Involvement of nails is not part of the assessment.

Based on this scale, subjects will be considered as IGA mod 2011 0 or 1 responder if they achieve a score of 0 or 1 and improve by at least 2 points on the IGA scale compared to baseline.

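### The SAP does not say which record in a visit window IGA mod 2011 uses; read naturally it is the worst one, while PASI uses the closest, so IGA 0/1 rates depend on how often patients make unscheduled visits

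*SAP*

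**What the plan says.** SAP 1.4.4 maps every assessment into a window and accepts that "due to unscheduled visits, several assessments of a subject may fall in a particular visit window". SAP 1.4.5 then gives three selection rules for post-baseline windows, which apply unless something else is specified:

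- "for *quantitative variables*, the *closest* to the actual visit is chosen", with the earlier record taken in a tie.
- "for *qualitative variables*, the *worst* record is selected". The only example is urine protein.
- "in case qualitative variables are based on quantitative variables, e.g. PASI 75 response", the response follows the visit selected for the underlying quantitative variable.

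No rule specific to IGA appears in SAP 1.8.1.2 or 1.8.7. IGA at baseline is listed by category label in SAP 1.5.2 ("Baseline IGA mod 2011 score (almost clear, mild disease, moderate disease, severe disease"). In Table 1-7, the row "IGA mod 2011 0 or 1 response from Week 28 to Week 52 (or Week 60" is marked only for categorical summaries and risk differences. A responder must score 0 or 1 and also "improve by at least 2 points on the IGA scale compared to baseline" (SAP 1.8.1.2).

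Protocol Section 6 says that "patients may be seen at an unscheduled visit, eg, if they experience deterioration of psoriasis or suspected AEs". Table 6-1 marks PASI, IGA and EQ-5D in the unscheduled column, at the investigator's discretion. Protocol 5.4 has patients self-administer open-label, while a blinded assessor does all PASI and IGA ratings in Treatment Period 2.

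**The concern.** A worst-record rule suits safety findings. Applied to an efficacy rating, it changes the endpoint from response at the visit to no observed non-response in the window, and what is observed depends on how often the patient is seen. Unscheduled visits are offered for worsening psoriasis, and patients know their dosing interval when they decide whether to ask for one. The plan itself allows for up to 7 points more loss of PASI 90 on 6-weekly dosing (Protocol 9.7), so unequal numbers of extra visits are plausible. Blinding the assessor does not remove this.

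IGA 0/1 at Week 52 is a protocol secondary endpoint, and SAP 1.8.7 gives risk differences between arms for it. It would be read beside PASI response rates that follow a different rule. For example, a patient rated IGA 2 at an unscheduled visit on Day 353, and IGA 0 with PASI 90 response at the Week 52 visit on Day 365, would be a PASI 90 responder and an IGA non-responder at the same analysis visit.

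Even if the worst-record reading is not what was meant, two programmers could derive this endpoint differently and both could cite SAP 1.4.5.

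**Working it through.** The plan gives no figure for this rule, so there is none to reproduce. The check is a reading of the rules, followed by an illustration on assumed inputs.

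**Step 1: which rule applies to IGA.** PASI has a continuous row in Table 1-7 as well as response rows, so PASI responses fall under the third rule and use the closest record. IGA has no continuous row and is described by labels from clear to severe, so it falls most naturally under the worst-record rule. Against that, the responder definition subtracts points on a 0–4 score. Someone could treat the score as quantitative and take the closest record under the third rule. Both readings are possible; the first fits the rest of the SAP better.

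**Step 2: which records compete.** From Week 8 the windows in Table 1-3 are contiguous 28-day blocks, so from Week 28 to Week 48 an unscheduled visit on either side of the scheduled one can count. Week 52 is different: its window is Days 352–379, but SAP 1.4.3 sends everything after the Week 52 visit to Week 60. With that visit on Day 365, only Days 352–364 (13 days) can supply a competing record.

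**Step 3: size in a full window.** Let p be the IGA 0/1 rate at the scheduled visit, u the share of patients with an extra record in the window, and q the chance that the extra record is a non-response when the scheduled one is a response. The worst-record rule lowers the rate by p × u × q. With p and q equal in arms A and B, the gap is p × q × (uB − uA). For p, 0.64 is the historical Week 52 IGA 0/1 rate in all patients (Protocol 1.1), and 0.818 is borrowed from PASI 90 maintenance (Protocol 9.7). The values of u and q are assumptions.

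| p | q | u, arms A and B | Fall in A (points) | Fall in B (points) | Gap (points) |
|---|---|---|---|---|---|
| 0.64 | 0.3 | 1%, 3% | 0.19 | 0.58 | 0.38 |
| 0.818 | 0.5 | 2%, 6% | 0.82 | 2.45 | 1.64 |
| 0.818 | 0.5 | 5%, 15% | 2.04 | 6.13 | 4.09 |
| 0.818 | 0.8 | 5%, 15% | 3.27 | 9.82 | 6.54 |
| 0.818 | 0.5 | 5%, 5% | 2.04 | 2.04 | 0 |

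Gaps are computed before rounding. For scale, the standard error of a rate difference at the planned 570 per group is √(2 × 0.818 × 0.182 / 570) = 0.0229, or about 2.3 points.

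**Step 4: both rules compared, and Week 52.** A simulation used p = 0.818 and q = 0.5 in both arms. The scheduled visit fell within ±5 days of its nominal day and the extra record on a random day in the 28-day block. Extra records not before the Week 52 visit were dropped, and closeness was measured from the nominal day.

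| Window | u, arms A and B | Worst rule: falls, gap | Closest rule: falls, gap |
|---|---|---|---|
| Week 40 | 2%, 6% | 0.79 and 2.38, gap 1.59 | 0.15 and 0.44, gap 0.29 |
| Week 40 | 5%, 15% | 1.96 and 5.93, gap 3.97 | 0.36 and 1.10, gap 0.74 |
| Week 52 | 2%, 6% | 0.38 and 1.14, gap 0.76 | 0.08 and 0.24, gap 0.16 |
| Week 52 | 5%, 15% | 0.94 and 2.85, gap 1.91 | 0.20 and 0.59, gap 0.39 |

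The Week 52 gap under the worst rule is about half the Week 40 gap (0.76/1.59 = 0.48; 1.91/3.97 = 0.48).

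**Step 5: EQ-5D.** The dimensions are tabulated as categories, so they take the worst record; the utility index and VAS are continuous and take the closest. For measures not collected at every visit, SAP 1.4.4 merges windows: its Week 36 example runs from Day 212 to Day 295, which is 295 − 212 + 1 = 84 days. The dimension table and the index for one analysis visit can therefore come from different questionnaires.

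**The case against.** The strongest reply is that the SAP never puts IGA under the worst-record rule. A reader might infer that it does so expressly. It does not, and the points-based responder definition makes the closest-record reading arguable. This stands: the defect is an unclassified variable whose more natural classification is the troublesome one.

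A reader might also infer a known bias against 6-weekly dosing. The documents do not support that. They give no unscheduled-visit rates by arm, scheduled visits are the same in every arm, and unscheduled visits also cover suspected adverse events. If extra visits and discordant ratings are equally common, the gap is zero. An IGA of 2 from a blinded assessor is also a real observation, so part of any gap could be genuine. If 6-weekly patients did come in more often, the rule would work against the experimental arm among PASI 90 responders. More extra visits on 4-weekly dosing in the partial-responder pool would instead favour the experimental arm.

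Week 52 is less exposed than a full 28-day window suggests. Besides the cut-off in SAP 1.4.3, all four groups have their last planned dose at Week 48, so time since last dose is the same, although earlier exposure differs. The fuller effect falls on Weeks 28–48, which SAP Table 1-6 lists as additions to the protocol.

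Finally, the closest rule is not fully immune (Step 4), and its reference point, the actual visit, is unclear. None of this answers the mismatch between IGA and PASI or the two possible derivations.

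**Conclusion.** The point holds as a gap in the SAP that affects secondary, descriptive results. Under the natural reading, IGA 0/1 uses the worst record in the window while PASI responses use the closest. That choice can only lower IGA 0/1, and lowers it more in an arm with more extra visits. The direction follows from the rule; the size cannot be derived from the documents. The 0.4 to 6.5 points in a full window rest wholly on the assumed p, q and u, and on equal true rates at the scheduled visit. Weeks 28–48 are mainly affected, Week 52 roughly half as much.

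It would be wrong to infer a threat to the main conclusions. The primary and key secondary endpoints are PASI 90 responses and so fall outside the worst-record rule. The time-to-loss analyses take the first visit with an observed loss (SAP Table 2-1), not a window selection. IGA 0/1 is outside the confirmatory hierarchy (SAP 1.8.6). The EQ-5D mismatch concerns contingency tables and its size is not estimated.

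**What to change.** Add to SAP 1.4.5:

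- IGA mod 2011 and IGA 0/1 response use the record from the visit selected for PASI in that window.
- EQ-5D dimensions use the questionnaire selected for the utility index.
- Closeness is measured from the scheduled day in Table 1-3.

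A count of unscheduled assessments by arm would show readers whether the choice mattered.

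The cost is a few sentences and a merge on the selected PASI visit, with no new data. The small downside is that IGA 0/1 rates may come out slightly higher, and so less conservative, than under the worst-record rule. The worst-record version can be kept as a sensitivity analysis.
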